COVER PAGE

Study Title: Modern Urodynamics System Efficacy (MUSE) Study

NCT: NCT05959655

Date of Document: 2023-06-28

1 Protocol Synopsis

Study Title	Modern Urodynamics System Efficacy
Short Title	MUSE Study
Study Sponsor	Bright Uro
Protocol Number	CIP-0005
Study Objective(s)	The objectives of the present study are to evaluate the feasibility, efficacy, and safety of the GUS for use in the clinic to collect vesical pressure data.
Study Design	This is a prospective, observational trial collecting vesical pressure (Pves) and flow from the GUS and cUDS system in patients with Lower Urinary Tract Symptoms (LUTS).
Phase	Phase 0
Estimated Study Period	Up to 24 months
Investigational Devices	Glean Urodynamics System (GUS)
Indications for Use/Intended Use	
Indications for Use: The GUS is indicated for standard Urodynamic tests such as Uroflowmetry (UF), Cystometrogram (CMG), Urethral Pressure Profile (UPP), and Micturition Studies (MS).
 
Intended Use: The GUS is a Urodynamic Analyzer system that is intended to quantify the pressure characteristics of the lower urinary tract. The system can be used to perform standard Urodynamic tests such as UF, CMG, UPP, and MS.
 
The major application of Urodynamics is the diagnosis of uncontrolled loss of urine (incontinence), abnormal urinary retention, or neurological cases of Micturition disorder. The device is intended to be used as medical diagnostic equipment.

Number of Subjects	Up to 50 subjects will be enrolled. Assuming a ~20% dropout rate, we expect 40 subjects (20 males and 20 females) to complete the study.
Duration of Study and Follow-up	Each subject will be in the study for up to 24 hours to complete ambulatory GUS.
Study Population	Patients with Lower Urinary Tract Dysfunction (LUTD) who are scheduled for cUDS studies.
Study Site(s)	Up to 6 sites in the United States
Inclusion Criteria	
 1. Male or female patient must be \geq 18 years of age 2. Patient must have a diagnosis of LUTD 3. Patient must be scheduled for or recommended for cUDS 4. Patient is able to tolerate 18Fr catheterization 5. Patient or patient's legally authorized representative is able to provide informed consent

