Study Endpoints	
Baseline Characteristics and Demographics (obtained from EMR or patient chart): Age, sex, prior urological conditions, reason for UDS, LUTD-related medications
 
Primary Endpoints: Success of Glean sensor insertions and removals, subjects experiencing a device-related Serious Adverse Event (SAE), and subject exhibiting compliance in terms of device and voiding diary usage.
 
Secondary Endpoints: Participant-reported outcomes (e.g., comfort, ease of use), successful transfer of GUS data from devices to clinician App and clinician web portal for clinician review.

Analyses	Success of Glean sensor insertions and removals will be calculated as percent of insertions and removals deemed successful by the clinician and subject.

	
Safety will be reported as the percent of subjects experiencing a device-related SAE. Rates of SAEs will be calculated on a per-subject, per-event, or per-person-year of follow-up basis. Exact binomial confidence intervals will be calculated for subject-based or event-based rates.
 
Likert scale outcomes will be summarized using frequencies and distributional statistics with binomial or normal approximation-based confidence intervals.

Study and Data Management	
Bright Uro [name] [contact] [contact] [contact]

Safety Monitoring	Site Investigators

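### The synopsis measures safety only by device-related SAEs, so non-serious harms from the Glean Sensor reach no adverse-event or safety endpoint

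*Combined protocol and SAP*

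**What the plan says.** The Study Objective(s) row of the Protocol Synopsis sets out to "evaluate the feasibility, efficacy, and safety of the GUS for use in the clinic". Three parts of the synopsis then decide how safety is measured.

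- **Study Endpoints.** The safety component of the primary endpoints is the device-related SAE. The other primary components are insertion and removal success, and compliance with the device and voiding diary. The secondary endpoints are participant-reported outcomes, such as comfort, and data transfer. No adverse event below the SAE level is named.
- **Analyses.** "Safety will be reported as the percent of subjects experiencing a device-related SAE". The sentence that follows, on rates, is also confined to SAEs. The interval method is given: "Exact binomial confidence intervals will be calculated for subject-based or event-based rates". The confidence level is not stated, and neither is the denominator for the safety percentage.
- **Number of Subjects.** "Up to 50 subjects will be enrolled", and "Assuming a ~20% dropout rate, we expect 40 subjects (20 males and 20 females) to complete the study".

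In Experimental Procedures, enrolment is step 1, cUDS is steps 4 and 5, and the Sensor is placed at step 15. The movement tests are step 18, the uroflowmeter void with PVR is step 24, removal by string is step 26, and discharge is step 27.

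**The concern.** The procedure passes a sheath and Sensor through the urethra after cUDS has already been done. The subject then moves about with the Sensor in the bladder, and it is withdrawn by its string. The foreseeable harms are mostly of a kind that would not usually meet the definition of serious: urethral pain, visible bleeding, or intolerance that leads to early removal. Step 12 itself allows for patients who are hypersensitive to pain and to insertion.

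Under the stated rule, each of these subjects counts as having no safety event. The study could report 0% on its safety measure while a sizeable share of subjects had non-serious, device-related harm, and nothing in the stated analysis would reveal it. For a short diagnostic procedure, that is the harm that patients and clinicians are most likely to meet.

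**Working it through.** **Inputs.** Up to 50 enrolled, about 20% dropout and 40 completers (Number of Subjects); exact binomial intervals (Analyses). The 95% two-sided level and all event counts below are assumptions, because the documents give none.

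**1. The plan's own figure.** 40 / (1 − 0.20) = 50, so enrolment and completers agree.

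**2. Where a non-serious harm would be recorded.** Each type of harm is set against the endpoints in the synopsis.

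| Harm (non-serious) | Device-related SAE | Other endpoint it might touch |
|---|---|---|
| Urethral pain | Not counted | Comfort rating; possibly the subject's view of insertion or removal success |
| Visible bleeding | Not counted | None directly; a completed insertion with bleeding can still be judged successful |
| Early Sensor removal for intolerance | Not counted | Possibly device compliance or removal success |

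The entries in the last column are indirect. None of those endpoints counts adverse events. PVR at step 24 gives some information on emptying, but it is measured before removal at step 26 and is not an endpoint.

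**3. What the SAE percentage can show.** For zero events in n, the exact two-sided 95% upper limit is 1 − 0.025^(1/n).

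- n = 40: 1 − 0.025^(1/40) = 0.088, or 8.8%.
- n = 50: 1 − 0.025^(1/50) = 0.071, or 7.1%.

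One-sided 95% limits, 1 − 0.05^(1/n), are 7.2% and 5.8%.

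**4. What an any-AE percentage could show.** For x events in n, the Clopper-Pearson limits are the 0.025 quantile of Beta(x, n − x + 1) and the 0.975 quantile of Beta(x + 1, n − x).

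| Illustrative count | n = 40: percent (95% CI) | n = 50: percent (95% CI) |
|---|---|---|
| 4 | 10% (2.8% to 23.7%) | 8% (2.2% to 19.2%) |
| 8 | 20% (9.1% to 35.6%) | 16% (7.2% to 29.1%) |

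The intervals are wide, but each excludes zero and bounds the rate from above, so the sample can describe non-serious harm if it is counted.

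**The case against.** The strongest reply is that the text available is only a synopsis. Definitions, collection of AEs and a safety population would normally stand in a protocol body, and exclusion criterion 2 points forward to CDC guidance that does not appear in this text. This stands as a limit on confidence. It does not remove the point, because the synopsis states what the safety measure will be, and that measure leaves out non-serious harm even if such harm is recorded elsewhere.

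A second reply is that pain or poor tolerance can lower comfort ratings, compliance, or insertion and removal success. That is right, so it would be wrong to say that these harms reach no endpoint at all. They reach no adverse-event or safety endpoint.

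Several stronger readings are tempting, and the documents do not support them.

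- *That the expected dropout of about 10 in 50 hides harm.* The figure is a planning allowance. Enrolment comes before urine testing, cUDS and Sensor insertion, so some subjects may leave before any Sensor is placed. No reasons for dropout are given.
- *That zero SAEs in about 40 subjects would say almost nothing.* It would argue against risks above about 9%, which is useful in a Phase 0 feasibility study. The planned exact interval would show the remaining uncertainty openly.
- *That the Sensor or sheath is 18Fr.* Inclusion criterion 4 asks only that the patient tolerate catheterization of that size. No device size is stated.

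**Conclusion.** The point holds in a limited form. Safety is an objective, and the synopsis measures it only by device-related SAEs. Non-serious device- or procedure-related harm therefore has no adverse-event or safety endpoint and could show only indirectly elsewhere.

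A reader might infer that the study cannot answer its safety objective at all. That goes too far: it can estimate serious device-related harm with an exact interval. On the text available, it cannot describe non-serious harm.

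The size of the gap cannot be computed, because the documents give no AE rates. At assumed rates of 10% or 20% in 40 subjects, 4 or 8 affected subjects would be missing from the safety result. The change should be made. Confidence is medium, since a fuller protocol may define or collect AEs beyond what the synopsis shows.

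**What to change.** Amend the Study Endpoints and Analyses rows as follows.

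1. Keep the percentage of subjects with a device-related SAE.
2. Add, as a safety endpoint, the percentage of subjects with any device- or procedure-related AE, serious or not, with the same exact binomial interval. State the confidence level.
3. Use as denominator all subjects in whom Glean insertion was attempted (up to 50), not only the 40 expected completers.
4. Count Sensor removal before the step 24 void as an event when an AE was the reason.
5. List each dropout with its reason and whether it came before or after an insertion attempt.

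The cost is wording in two rows and an AE entry on the case report form, with no extra visit or procedure. There are two downsides. The reported safety rate will look less favourable than an SAE-only rate. Subjects are discharged directly after removal (steps 26 and 27) and urine testing is listed only beforehand, so infection, retention or bleeding that appears later would still be missed. The report should state this limit.
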